### 6.4.2.4 Event Free Survival (EFS)

For a subject with none of these events as relapse, treatment failure or death, EFS is censored at the date of last relapse-free disease assessment (last relapse-free disease assessment date – first dose date +1). Subject without post-treatment disease assessment will be censored at randomization date.

Treatment failure includes those subjects who discontinued the treatment due to “progressive disease” or “lack of efficacy” without a previous response of CR, CRp, CRI or PR.

EFS will be presented in listing only.

### 6.4.2.5 Duration of Response

Duration of Response will be presented in listing only.

### 6.4.2.6 Progression Free Survival (MDS only)

PFS will be presented in listing only.

## 6.4.3 Analysis of Exploratory Endpoints

### 6.4.3.1 Biomarkers / Pharmacodynamics (*Not Applicable for China*)

WT1 RNA expression will be summarized by change from baseline at each time point. Selected immune cell phenotypes will be summarized by change from baseline at each time point by percentage. Gene mutations, immune cell phenotypes, anti-HLA antibodies and replication competent lentivirus (RCL) will be assessed and reported in listings.

## 6.5 Analysis of Safety

All analysis of safety will be presented overall and by dose level for SAF, unless specified otherwise. Safety data for the China cohort will be summarized separately.

### 6.5.1 Adverse Events

For the purpose of safety assessments in this study, events recorded during the pre-investigational period will be classified as Baseline Signs and Symptoms. All adverse events (AE) recorded on treatment including within 30 days from the last study treatment will be summarized.

Summaries and listings of SAEs and Serious TEAEs include SAEs upgraded by the sponsor based on review of the Sponsor's list of Always Serious terms if any upgrade was done.

The coding dictionary for this study will be MedDRA. It will be used to summarize AEs by SOC and PT. AEs will be graded using National Cancer Institute's Common Terminology Criteria for AEs (NCI-CTCAE).

An overview table will include the following details by phase, disease type, and dose level:

- Number and percentage of subjects with TEAEs
- Number and percentage of subjects with IP related TEAEs
- Number and percentage of subjects with TEAE leading to death
- Number and percentage of subjects with IP-related TEAE leading to death
- Number and percentage of subjects with serious TEAEs and Astellas upgraded serious TEAE
- Number and percentage of subjects with serious IP related TEAEs and Astellas upgraded serious IP related TEAE
- Number and percentage of subjects with TEAEs leading to permanent discontinuation of study IP
- Number and percentage of subjects with IP related TEAEs leading to permanent discontinuation of study IP

The number and percentage of subjects with TEAEs, as classified by SOC and PT will be summarized by phase and dose level. Summaries will be provided for:

- TEAEs
- IP related TEAEs
- serious TEAEs and Astellas upgraded serious TEAE
- IP related serious TEAEs and IP related Astellas upgraded serious TEAE
- TEAEs leading to permanent discontinuation of study IP
- IP related TEAEs leading to permanent discontinuation of study IP
- TEAEs leading to dose interruption
- TEAEs excluding serious adverse events that equal to or exceed a threshold of 5% in any dose level
- Frequency reported TEAEs that equal to or exceed a threshold of 5% in any dose level

The number and percentage of subjects with TEAEs, as classified by PT only, will be summarized by phase and dose level.

AE summary tables will include subject counts as opposed to AE counts. If a subject experiences more than one episode of a particular AE, that subject will be counted only once for that event. If a subject has more than one AE that code to the same preferred term, the subject will be counted only once for that preferred term. Similarly, if a subject has more than one AE within a body system, the subject will be counted only once in that body system.

The number and percentage of subjects with TEAEs, as classified by SOC and PT will also be summarized by NCI-CTCAE severity grade and by relationship to study drug. In the subject count, if a subject has multiple TEAEs with the same SOC or PT, but with differing severity grade or relationship, then the subject will be counted only once with the worst severity grade and highest degree of relationship, however, if any of the severity grade or relationship values are missing then the subject will be counted only once with missing severity grade or relationship. The number and percentage of subjects with CTCAE grade 3 or higher TEAE and number and percentage of subjects with CTCAE grade 3 or higher IP related TEAE will be summarized by phase and dose level.

The number and percentage of subjects with TEAEs, as classified by SOC and PT will be summarized by dose level for safety analysis set.

All AEs, deaths, SAEs, withdrawals due to adverse events, and AEs for subjects will be displayed in listings.

The list of adverse events to be summarized may change during the course of the study due to ongoing pharmacovigilance.

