7.3.2 Method of Detecting Adverse Events and Serious Adverse Events

The methods of recording, evaluating and assessing seriousness, causality and severity of AEs and SAEs are described in [[Appendix 12.4 AEs: Definitions and Procedures for Recording, Evaluating, Follow-up or Reporting](#)]. Care will be taken not to introduce bias when detecting AEs and/or SAEs. Open-ended and nonleading verbal questioning of the subject is the preferred method to inquire about AE occurrences.

An AE with a change in severity is recorded as a new AE.

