9.5.1 Adverse Events

AEs will be coded using MedDRA v21.1 and graded using NCI CTCAE 5.0.

A treatment-emergent adverse event (TEAE) is defined as an AE observed after starting administration of the IP and 30 days after the final administration of IP. An IP-related TEAE is defined as any TEAE with a causal relationship assessed as “yes” by the investigator.

The number and percentage of subjects with TEAEs, drug-related TEAEs, serious TEAEs, drug-related serious TEASs, TEAEs leading to withdrawal of treatment and drug related

TEAEs leading to withdrawal of treatment will be summarized by SOC, preferred term and treatment group. The number and percentage of TEAEs by severity will also be summarized. The worst severity will be summarized if the same AE is recorded more than once for a subject.

AE data will be listed.

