## **4.6 DLT Evaluation Analysis Set**

The DLT Evaluation Analysis Set (DEAS) is defined as all subjects in SAF by excluding the subjects who meet any of the following criteria:

- Subject is discovered to have enrolled without fully satisfying eligibility criteria.
- Subject received less than the planned dose in cycle 1 for reasons other than DLT.
- Subject has no DLT and withdraws from the study before the end of DLT evaluation period.

The DEAS will be used for the analysis of DLT data.

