### 5.2.3 Safety Endpoint: Adverse Events

AEs will be coded using MedDRA v26.0 and graded using NCI CTCAE 5.0. A treatment-emergent adverse event (TEAE) is defined as an AE observed after starting administration of the IP and 30 days after the final administration of IP. An IP-related TEAE is defined as any TEAE with a causal relationship assessed as “yes” by the investigator or with missing assessment of the causal relationship. The number and percentage of subjects with TEAEs, IP-related TEAEs, serious TEAEs, IP-related serious TEASs, TEAEs leading to withdrawal of treatment and drug related TEAEs leading to withdrawal of treatment will be summarized by SOC, preferred term and treatment group. The number and percentage of TEAEs by severity will also be summarized. The worst severity will be summarized if the same AE is recorded more than once for a subject. AE data will be listed.

If the adverse event occurs on Day 1 and the onset check box is marked “Onset after first dose of study drug” or the onset check box is left blank, then the adverse event will be considered treatment emergent. If the adverse event occurs on Day 1 and the onset check box is marked “Onset before first dose of study drug”, then the adverse event will not be considered treatment emergent. If a subject experiences an event both during the preinvestigational period and during the investigational period, the event will be considered as TEAE only if it has worsened in severity (i.e. it is reported with a new start date). All adverse events collected that begin within 30 days after taking the last dose of study drug will also be counted as TEAE.

Immune-related AE (irAE) and infusion related reactions (IRR) will be considered as Adverse Events of Special Interest (AEsi). The list of events classified as AEsi may change during the study due to ongoing pharmacovigilance.

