## 6 STATISTICAL METHODOLOGY

### 6.1 General Considerations

For continuous variables, descriptive statistics will include the number of subjects (n), mean, standard deviation, median, minimum and maximum. When needed, the use of other percentiles (e.g., 10%, 25%, 75% and 90%) will be reported in the relevant section. In addition, for plasma concentrations and continuous PK parameters, the coefficient of variation and the geometric mean will also be calculated. Frequencies and percentages will be displayed for categorical data. Percentages by categories will be based on the number of subjects with no missing data, i.e. will add up to 100%.

Summaries based on FAS and RAS (e.g. disposition, baseline and efficacy data) will be presented by planned treatment, unless specifically stated otherwise. Safety analysis and other summaries based on SAF, PKAS or PDAS will be presented by actual dose level received. Pharmacokinetic summaries based on PKAS and pharmacodynamic summaries based on PDAS will be presented by actual dose level received. Data for the China cohort will be summarized separately, by dose level.

All data processing, summarization, and analyses will be performed using SAS® Version 9.3 or higher on Unix. Specifications for table, figure, and data listing formats can be found in the TLF specifications for this study.

Baseline is defined as the last available measurement prior to the first dose of IP. Unless otherwise specified, all summaries will be presented overall, by dose level and by phase.

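### In the SAP 6.5.1 tables by grade and by relationship, one missing value displaces a subject's known worst grade or known relationship

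*SAP*

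**What the plan says.** SAP 6.5.1 covers the tables of treatment-emergent adverse events (TEAEs) by SOC and PT, split by CTCAE grade and by relationship to study drug. A subject with several events in the same SOC or PT is to be "counted only once with the worst severity grade and highest degree of relationship". The sentence then adds an exception: "if any of the severity grade or relationship values are missing then the subject will be counted only once with missing severity grade". It treats a missing relationship in the same way.

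The rules elsewhere differ:

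- **Severity.** Protocol 9.5.1 states: "The worst severity will be summarized if the same AE is recorded more than once for a subject". SAP 5.2.3 says the same. Neither has an exception for missing values.
- **Relationship, protocol 9.5.1.** "An IP-related TEAE is defined as any TEAE with a causal relationship assessed as" yes by the investigator. A blank is not included.
- **Relationship, SAP 5.2.3.** The definition is widened by the words "or with missing assessment of the causal relationship", so a blank counts as related.
- **Recording.** Protocol 7.3.2 states: "An AE with a change in severity is recorded as a new AE". More than one record per subject and term is therefore expected.

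SAP 6.5.1 also plans counts of subjects with grade 3 or higher TEAEs, overall and IP-related. These stand in a separate sentence that does not mention missing values.

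**The concern.** A missing grade on one record says nothing against a grade that was recorded on another. If a subject has a documented grade 4 event, the worst grade is at least 4 whatever the blank record would have said. The exception discards that information and shows the subject as unknown. Because it works at SOC level as well as PT level, a blank on one preferred term can also remove a known high grade on a different term in the same SOC.

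For relationship, a blank receives three different treatments in the two documents. Tables built from the same records could then give different counts of related events with nothing to explain the difference.

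Safety is a primary objective and the groups are small. Stage 1 of phase 2 has 12 subjects per dose level and disease type, so moving one subject out of the high-grade rows is visible.

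**Working it through.** The plan states no figure for this point, so there is none to reproduce. The check compares the rules, then sizes the effect under assumptions.

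**1. The rules applied to one subject with two records in the same PT**

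| Records | First clause of SAP 6.5.1 | Exception in SAP 6.5.1 | SAP 5.2.3 | Protocol 9.5.1 |
|---|---|---|---|---|
| Grade 4 and ungraded | Grade 4 | Missing | Worst severity: grade 4 | Worst severity: grade 4 |
| Related yes and blank | Related | Missing | Related | Related |
| Related no and blank | Not settled | Missing | Related | Not related |

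In the first two rows the exception gives a result that no other rule gives. In the third row, three rules give three answers.

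The worst-severity rule in protocol 9.5.1 and SAP 5.2.3 concerns the same event recorded more than once, which is closest to PT level. The conflict with those sections is direct there. At SOC level the exception conflicts with the first half of its own sentence.

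**2. How often a subject would be affected**

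Inputs, all assumed:

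- m is the share of records with a missing value. The documents give no rate.
- k is the number of records a subject has in the PT or SOC.
- Missingness is independent between records.

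The chance that at least one of k records is missing is 1 − (1 − m)^k. At m = 1%:

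- k = 2: 1 − 0.99² = 2.0%
- k = 3: 1 − 0.99³ = 3.0%
- k = 10: 1 − 0.99¹⁰ = 9.6%

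| m | k = 2 | k = 3 | k = 10 |
|---|---|---|---|
| 0.5% | 1.0% | 1.5% | 4.9% |
| 1% | 2.0% | 3.0% | 9.6% |
| 2% | 4.0% | 5.9% | 18.3% |
| 5% | 9.8% | 14.3% | 40.1% |

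At m = 0 every entry is zero. Two or three records is the realistic range for one PT; ten is an illustration for a SOC. The table gives the chance of any missing value. The chance that a known high grade is displaced is smaller, because the subject must also have such a grade.

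**3. What one affected subject does to a table (hypothetical)**

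Three subjects have a known grade 3 or higher event in one PT, and one of them also has an ungraded record there. The by-grade rows then show 3 − 1 = 2 subjects at grade 3 or higher, and one in the missing row.

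- 12 subjects: 2/12 = 16.7% instead of 3/12 = 25.0%
- 52 subjects: 2/52 = 3.8% instead of 3/52 = 5.8%

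**The case against.** The strongest reply is that the rule will rarely be triggered. Protocol 12.4.3 obliges the investigator to assess causality for every event. Protocol 12.4.4 requires grading and supplies a fallback scale for events outside CTCAE. Protocol 10.1 makes sites responsible for complete case report forms and for resolving queries. The missing rate may well be low, and the upper part of the range above should not be read as a forecast. This limits the size of the effect but does not reconcile the rules.

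The reply also holds that known events survive elsewhere. The subject stays in the SOC and PT totals and in the listings. Under SAP 5.2.3 both a yes and a blank count as IP-related, so the dedicated IP-related tables do not lose a related event. This stands, and it confines the point to the by-grade and by-relationship tables.

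Three stronger readings are tempting, and the documents do not support them:

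- **That the grade 3 or higher counts lose events too.** They are planned in their own sentence without a missing-value rule. Read plainly, they would still show 3/12 in the example. The SAP should say so, but a loss there cannot be asserted.
- **That an affected subject also leaves the denominator.** SAP 6.1 says: "Percentages by categories will be based on the number of subjects with no missing data, i.e. will add up to 100" percent. That convention suits percentages that sum to 100. Adverse event incidences do not, SAP 6.5 sets the safety analysis set as the default, and SAP 6.5.1 itself provides for a missing category.
- **That dose-limiting toxicities (DLTs) are hidden in the same way.** The DLT evaluation set has exclusions not tied to absence of a DLT, such as "Subject is discovered to have enrolled without fully satisfying eligibility criteria". That is a separate, defined analysis set. DLT details remain in listings and narratives (protocol 9.5.7), the events remain in the safety-set tables, and the Dose Escalation and Safety Committee considers all available safety findings (protocol 10.4.1). An all-treated DLT count would be a reporting preference; nothing here shows an error in that set.

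**Conclusion.** The exception in SAP 6.5.1 is wrong as written. It replaces a known worst grade or a known relationship with missing, against the first half of its own sentence, the worst-severity rule in protocol 9.5.1 and SAP 5.2.3, and the treatment of missing causality in SAP 5.2.3. This conclusion needs no assumption about rates.

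The size does. It is zero if no value is missing and probably small if completeness is good: 2.0% to 3.0% of subjects with 2 to 3 records in a PT at an assumed 1% of records missing, with independence. In a group of 12, one displaced subject changes the by-grade rows by 1/12, or 8.3 percentage points. No effect on dose decisions, on the dedicated IP-related tables or on the listings is claimed.

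**What to change.** In SAP 6.5.1:

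- Count each subject at the worst non-missing grade within the SOC or PT. Use the missing category only when all of that subject's grades there are missing.
- Footnote how many of the counted subjects also have an ungraded record.
- Treat a missing relationship as related, in line with SAP 5.2.3. Report this in the clinical study report as a change from protocol 9.5.1, which counts only a yes.
- State that the same rule applies to the grade 3 or higher tables.

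The cost is a few lines of SAP text, one footnote and the matching programming. No new data are needed. There are two downsides. The worst known grade understates severity if the ungraded record was in fact worse; the footnote shows how many subjects this could concern. Counting missing causality as related may overstate relatedness.

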### **6.5.2 Adverse Events of Special Interest (AEsi)**

The number and percentage of subjects with Adverse Events of Special Interest (AEsi) such as IRR and irAE, and as classified by SOC and PT, will be summarized overall and by dose level.

An IRR overview table will include the following details by phase and dose level:

- Number and percentage of subjects with IRR TEAEs
- Number and percentage of subjects with IRR IP related TEAEs
- Number and percentage of subjects with serious IRR TEAE
- Number and percentage of subjects with IP-related IRR TEAE
- Number and percentage of subjects with IRR TEAE leading to death
- Number and percentage of subjects with IP related IRR TEAE leading to death
- Number and percentage of subjects with IRR TEAEs leading to permanent discontinuation of study IP
- Number and percentage of subjects with IP related IRR TEAEs leading to permanent discontinuation of study IP
- Number and percentage of subjects who died

An irAE overview table will include the following details by phase and dose level:

- Number and percentage of subjects with irAE TEAEs
- Number and percentage of subjects with irAE IP related TEAEs
- Number and percentage of subjects with serious irAE TEAE
- Number and percentage of subjects with IP-related irAE TEAE
- Number and percentage of subjects with irAE TEAE leading to death
- Number and percentage of subjects with IP related irAE TEAE leading to death
- Number and percentage of subjects with irAE TEAEs leading to permanent discontinuation of study IP
- Number and percentage of subjects with IP related irAE TEAEs leading to permanent discontinuation of study IP
- Number and percentage of subjects who died

### **6.5.3 Clinical Laboratory Evaluation**

The baseline visit is the last available measurement prior to the first dose of IP.

Quantitative clinical laboratory variables, i.e., hematology and biochemistry will be summarized using mean, standard deviation, minimum, maximum and median by phase and dose level at each visit. Additionally, a within-subject change will be calculated as the post-baseline measurement minus the baseline measurement and summarized in the same way.

Laboratory results will also be graded using NCI-CTCAE, where possible. Following the [Table 5](#) in Section 5.2.4, parameters that have criteria available for both low and high values, i.e., hypo- and hyper-, will be summarized for both criteria. The same subject can be counted for both values if the subject has different laboratory values meeting each criterion.

NCI-CTCAE grade of laboratory evaluations on hematology and chemistry will be summarized by number and percentage of subjects for each visit. Shift tables of NCI-CTCAE grade change from baseline to worst post-baseline grade will also be presented.

Laboratory results based on central assessment will be used for summaries as described above. Laboratory results based on local assessment and bone marrow results will be listed only.

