2.1.2 Summary of Key Safety Information for Investigational Product

2.1.2.1 Potential Risk

No studies with ASP7517 in humans have been conducted yet. The potential risks described below are based on ASP7517 nonclinical studies and clinical data from compounds with similar mechanism of action or composition. The management of toxicities should be based on institutional standard of care, published guidelines, as well as on investigator judgment, the protocol instructions regarding risk monitoring, and interruption or discontinuation of investigational product (IP) treatment.

Table 6 Potential Safety Concern of ASP7517

Key Safety Targets	Key Observations	Relevance to Human Usage
Liver	Increased liver weight, increased AST and ALT, emboli, hepatocyte focal necrosis, mixed inflammatory cell infiltration, microgranuloma, granulomatous inflammation (at $\geq 1 \times 10^5$ cells/kg); mononuclear cell aggregation, pigment laden macrophage infiltration (at $\geq 1 \times 10^7$ cells/kg)	Possible risk
Spleen	Increased spleen weight (at $\geq 1 \times 10^5$ cells/kg); extramedullary hematopoiesis (at $\geq 1 \times 10^6$ cells/kg)	Possible risk
Circulatory system	Emboli in the spleen and liver (at $\geq 1 \times 10^5$ cells/kg)	Possible risk
Kidney	Increased creatinine, tubular basophilia, mononuclear cell infiltration (at $\geq 1 \times 10^6$ cells/kg)	Possible risk
Hematology	Decreased platelet count 1 day after dose, increased platelet count 7 days after dose (at $\geq 1 \times 10^5$ cells/kg)	Possible risk
Pancreas	Focal necrosis (at 1×10^8 cells/kg)	Low potential risk
Urinary bladder	Mononuclear cell infiltration (at 1×10^8 cells/kg)	Low potential risk
Epididymis	Interstitial fibrosis and granuloma (at 1×10^8 cells/kg)	Low potential risk
Tumorigenicity	No colony formation in soft agar test No human cells (ASP7517) detected within 2-weeks in NOG mice after a dose of 1×10^8 cells/kg	Low potential risk
Embryo-fetal development	No embryo-fetal development studies have been performed to date	Unknown

ALT: alanine aminotransferase; AST: aspartate aminotransferase; NOG: NOD.Cg-Prkdcscid Il2rgtm1Sug/Jic.

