2.1.2.1.1 Liver

Preclinical studies demonstrated that the liver could be the target organ of toxicity for ASP7517, which is related to the activation of an innate immune response by presenting α -GalCer linked to CD1d on the surface of ASP7517 to natural killer T (NKT) cells. The activation of NKT cells is thought to be responsible for the hepatic injury induced with ASP7517. The hepatic findings could be monitored (increased AST and ALT 1 day after administration) and were completely reversed by 28 days after ASP7517 administration. The adverse events (AEs) in mice included increased liver weight, AST and ALT elevation, emboli, hepatocyte focal necrosis, mixed inflammatory cell infiltration, microgranuloma, granulomatous inflammation, mononuclear cell aggregation and pigment laden macrophage infiltration. Close monitoring of liver function and toxicities is required during clinical studies.

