2.1.2.1.3 Kidney

Increased serum creatinine was seen 1 day after the first dose. This finding was completely resolved 7 days after the first dose. In addition, histological assessment showed basophilic tubules and infiltration of mononuclear cells 7 days after the second dose. These histological findings were completely resolved 28 days after the second dose. The presence of basophilic tubules is interpreted as regeneration of renal tubules. The standard monitoring of kidney function parameters (creatinine, blood urea nitrogen) is recommended in clinical studies.

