2.1.2.1.6 Infusion-related Reactions

In nonclinical studies with ASP7517, infusion-related reactions (IRRs)/cytokine-release syndrome (CRS) were not seen. However, there are potential toxicities with intravenous infusion immunotherapy and the exact mechanism causing standard infusion reactions is unclear, but most reactions appear to arise from cytokine release from immune-mediated mechanisms [Lee et al, 2014].

The symptoms and signs associated with a standard infusion reaction include fever, shaking chills, flushing and/or itching, changes in heart rate and blood pressure, shortness of breath or chest discomfort, pain in back or abdomen, nausea, vomiting and/or diarrhea and skin rash.

In addition to the signs and symptoms associated with a standard infusion reaction, CRS may result in neurologic signs and symptoms such as mental status changes, confusion and delirium. Renal and hepatic manifestations may include azotemia, elevated transaminases and hyperbilirubinemia, respectively. Coagulation parameters maybe also be affected and manifested by elevated D-dimer and hypofibrinogenemia, with or without bleeding. In addition, tumor lysis syndrome may also be associated with CRS [Lee et al, 2014]. Patients should be closely monitored for IRRs and CRS and appropriately managed per standard of care.

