3 STUDY OBJECTIVE(S) AND ENDPOINT(S)

The study objectives and endpoints for this study are provided in [Table 7](#).

Table 7 Study Objectives and Endpoints

Objective(s)	Endpoint(s)
Primary	
• To evaluate the safety and tolerability of ASP7517• To determine the RP2D and/or the MTD of ASP7517 (phase 1)• To evaluate the clinical response of ASP7517 
• Safety and tolerability as noted by: DLTs, AEs, SAEs, laboratory test results (serum, chemistry, hematology, coagulation, and urinalysis, pregnancy test) ECGs, vital signs, physical exams and ECOG performance status scores• CRc rate for subjects with R/R AML and (CR + BM CR + PR) rate for R/R higher risk MDS (phase 2)
Secondary	
• To evaluate other measures of anticancer activity of ASP7517 
• Duration of remission• EFS• OS• CR, best response (CRc + PR) and CRh rates for subjects with R/R AML• CR, HI and objective response (CR + BM CR + PR + HI) rates for subjects with R/R higher risk MDS
Exploratory	
• To evaluate potential genomic, proteomic and/or other biomarkers that may correlate with treatment outcome• To evaluate pharmacodynamic activities of ASP7517• To evaluate pharmacokinetics of ASP7517, which is determined by the kinetics of the cells 
• Exploratory biomarkers that may correlate with treatment outcome of ASP7517• Pharmacodynamic effects of ASP7517, such as changes in:
○ Cytokine expression and secretion (e.g., IFNg)○ WT1-specific T lymphocytes (e.g., cytotoxic T lymphocytes)○ Immune cell populations (NKT cells, NK cells, etc.)• Cellular DNA load and kinetic parameter estimates for ASP7517

AE: adverse event; AML: acute myeloid leukemia; BM: bone marrow; CR: complete remission; CRc: composite complete remission; CRh: complete remission with partial hematologic recovery; DLT: dose limiting toxicity; ECG: electrocardiogram; ECOG: Eastern Cooperative Oncology Group; EFS: event-free survival; IFNg: interferon gamma; HI: hematologic improvement; MDS: myelodysplastic syndrome; MTD: maximum tolerated dose; NK: natural killer; NKT: natural killer T; OS: overall survival; PR: partial remission; R/R: relapsed/refractory; RP2D: recommended phase 2 dose; SAE: serious adverse event; WT1: Wilms' tumor 1 protein.

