9.5.2 Laboratory Assessments

For quantitative clinical laboratory measurements (hematology and biochemistry), descriptive statistics will be used to summarize results and change from baseline by dose level and time point.

Shifts from baseline to the worst grade based on NCI CTCAE 5.0 during the treatment period in clinical laboratory tests will be tabulated.

Laboratory data will be listed.

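### Coagulation is part of the primary safety endpoint, but the laboratory summaries leave it out; D-dimer and fibrinogen most likely reach listings only

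*SAP*

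**What the plan says.** Protocol Table 7 (section 3) defines the primary safety endpoint to include "laboratory test results (serum, chemistry, hematology, coagulation, and urinalysis, pregnancy test". Protocol 2.1.2.1.6, on infusion reactions and cytokine-release syndrome (CRS), says: "Coagulation parameters maybe also be affected and manifested by elevated D-dimer and hypofibrinogenemia, with or without bleeding". The coagulation panel has its own row in the treatment-period schedules (protocol Tables 1 and 2). SAP 5.2.4 and SAP Table 5 list five tests in it: aPTT, INR, PT, fibrinogen and D-dimer.

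The analysis sections are narrower. Protocol 9.5.2: "For quantitative clinical laboratory measurements (hematology and biochemistry), descriptive statistics will be used". SAP 6.5.3: "Quantitative clinical laboratory variables, i.e., hematology and biochemistry will be summarized using mean, standard deviation, minimum, maximum and median". Within-subject change from baseline is summarised in the same way, so it has the same scope. By-visit tables of CTCAE grade name hematology and chemistry. Shift tables to the worst grade name no panel. SAP 6.5.3 also says that centrally assessed results feed the summaries and that local results are only listed.

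**The concern.** The SAP's parenthesis defines which panels are summarised; it does not give examples. Followed exactly, a panel that belongs to the primary safety endpoint, and that contains the two tests the protocol links to CRS, is collected at repeated visits and then left out of the tables that would show its course.

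What is at stake is description by dose. A listing shows each subject's values but does not show whether D-dimer rises or fibrinogen falls after dosing, or whether the change is larger at higher dose levels. In an open-label dose-finding and expansion study with safety as a primary objective, that is a gap in the main report.

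**Working it through.** The documents give no figure to reproduce. The check is which planned outputs each coagulation test can enter.

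| Planned output | Panels named | Coagulation included? |
|---|---|---|
| Descriptive statistics and change from baseline (SAP 6.5.3, protocol 9.5.2) | Hematology, biochemistry | No |
| CTCAE grade counts by visit (SAP 6.5.3) | Hematology, chemistry | No |
| Shift to worst grade (SAP 6.5.3, protocol 9.5.2) | None; a grade is needed | Depends on SAP Table 5 |
| Liver table (SAP 6.5.3.1) | ALT, AST, ALP, bilirubin | No |
| Laboratory summary (protocol synopsis) | None | Neither excluded nor specified |
| Listings (protocol 9.5.2) | All laboratory data | Yes |

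**SAP Table 5.** The grading column shows three coagulation entries (Hyper, Hyper, N/A) for five tests. Read in order, they fall on aPTT, INR and PT, leaving fibrinogen and D-dimer with none. The table is broken in the text available, so this mapping is uncertain.

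**Count on that reading.**
- By-visit or change-from-baseline summary: 0 of 5 tests.
- Shift table: at most 2 of 5 (aPTT, INR).
- Listings only: 5 − 2 = 3 of 5 (PT, fibrinogen, D-dimer), including both tests named in protocol 2.1.2.1.6.

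If the mapping is wrong and fibrinogen or D-dimer does carry a grade, that test could enter a shift table. The 0 of 5 does not depend on the mapping.

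**Local versus central.** Protocol 7.2.2 and 10.1 have safety samples analysed in the institution's laboratory, with the results sent for centralised data entry. SAP 6.5.3 summarises central results and only lists local ones. Read literally, inserting coagulation into the SAP sentence would still leave it in listings. The same reading would catch hematology and chemistry.

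**Timing, as a limit on interpretation.** Days after dose = visit day − 1.
- Cycles 1 and 2 of phase 2 (Table 2): post-dose samples on days 2, 8, 15 and 22, that is 1, 7, 14 and 21 days after dosing.
- Cycles 3 to 6: day 1 is predose, so the only post-dose sample before the next cycle or the end-of-treatment visit is day 15, which is 14 days after dosing. With a ±1 day window this is 13 to 15 days. If the dose is given 3 days late and day 15 is counted from the scheduled day 1, the earliest is 14 − 1 − 3 = 10 days. The window row is also broken, so these ranges are approximate.

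Four of the six possible cycles therefore have no scheduled post-dose sample in the first 7 days.

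**The case against.** The strongest reply is that coagulation is not really lost. The synopsis promises summaries of laboratory parameters without naming panels. The shift tables are unrestricted. Everything is listed. Clinically significant abnormalities not due to the underlying disease are reported as adverse events (protocol 12.4.1.1) and so reach the SAP 6.5.1 tables. This stands in part: it is too strong to say that the trial does not analyse coagulation at all. But adverse-event tables show only what investigators judged significant, and the synopsis wording conflicts with the two detailed sections, so an edit is needed either way.

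A reader might infer three stronger points that the documents do not support:

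- *Coagulation is collected to follow the embolic risk.* Protocol Table 6 lists "Emboli in the spleen and liver" as a possible risk, but nothing ties coagulation tests to it. Protocol 2.1.2.1.4, which reports the spleen emboli, recommends hematology. The mouse doses at which emboli were seen therefore do not measure what is lost here.
- *The adverse events of special interest wrongly omit embolic events.* SAP 5.2.3 says that the list may change, and SAP 6.5.2 gives its two groups as examples. Further groups would be a preference.
- *The lighter sampling in cycles 3 to 6 is an error.* It is a design choice, and extra tests are left to institutional practice (protocol 7.2.2). The time course comes from mice after a first or second dose. For creatinine, "This finding was completely resolved 7 days after the first dose" describes the first dose only. For platelets the documents disagree: protocol 2.1.1.3 has signs of recovery at 7 days and full recovery by day 28, while 2.1.2.1.2 has counts above baseline at 7 days.

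**Conclusion.** The point holds as a gap in the analysis text. A named component of the primary safety endpoint has no by-visit or change-from-baseline summary in either detailed analysis section. D-dimer and fibrinogen most likely reach listings only. The first statement rests on the wording of SAP 6.5.3 and protocol 9.5.2. The second also rests on reading SAP Table 5 in order.

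The size is modest: five tests without descriptive tables, probably three of them in listings only. No efficacy result, error rate or sample size is affected. It is worth correcting because the data are already collected and the edit is small.

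The timing check supports one limit on interpretation and no more: cycle 3 to 6 laboratory tables cannot show changes in the first days after dosing. That is not a finding that the schedule is wrong.

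**What to change.** 1. In SAP 6.5.3 and protocol 9.5.2, extend the scope to *hematology, biochemistry and coagulation*.
2. Summarise aPTT, INR, PT, fibrinogen and D-dimer by dose level and visit with change from baseline, including predose to day 2 in cycles 1 and 2.
3. For D-dimer and fibrinogen, count subjects outside the laboratory reference range at the worst post-baseline value.
4. Define central assessment in SAP 6.5.3, and state that locally analysed results submitted for centralised data entry are the ones summarised.
5. Add one sentence saying that cycle 3 to 6 laboratory tables rest on predose day 1 and day 15 samples and cannot show changes in the first days after dosing.
6. Reconcile protocol 2.1.1.3 and 2.1.2.1.2 on platelet recovery.

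The cost is a few tables and short wording changes, with no new sampling. D-dimer may already be abnormal at baseline in this population. That is an assumption, since the documents give no baseline values. The D-dimer tables should therefore be read as change from baseline, and the reference-range counts shown with baseline status.
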